Standard MBSR approaches also pose a number of barriers at the patient-level, which can run counter to the VHA's goal of providing Veteran-centered care, and impede patient engagement, adherence, and maintenance, thereby reducing treatment effects. First, the time commitment of standard MBSR (classroom attendance, including travel time, and home practice requirements of 45 minutes daily) makes these approaches inaccessible or unsustainable for many. This problem is reflected in published studies by extremely low adherence and high attrition rates (up to 50% in some cases). Moreover, setting unrealistically high expectations for home meditation practice is likely counterproductive to establishing consistent, daily meditation practice, according to behavioral change theory. Low participation coupled with low adherence limit the reach and effectiveness and ultimate impact for pain patients. Additionally, access barriers exist for many Veterans who are not able to easily travel to the main VHA facilities where MBIs are offered. Qualitative research on barriers to MBIs (including two studies of Veterans) provide converging evidence that time demands (classroom attendance and practice requirements) pose a major barrier. This includes affecting the likelihood of enrolling in and completing MBIs and adhering to home practice requirements. Time-intensive programs, which do not provide tools for incorporating mindfulness practice into one's everyday life in the face of competing demands, may also negatively affect participants' ability to maintain the skills they learn in 8 weeks of instruction. For mindfulness practice to be a useful self-management approach and to have meaningful effects on outcomes important to patients, patients need to be able to continue their daily practice well beyond the 8-week intervention period, and to continue to use mindfulness skills in daily life, particularly when experiencing cues (such as pain and other stressors) that trigger maladaptive responses and behaviors. MBIs that include readily accessible tools and resources that encourage long term use are much needed.

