#### Measures

#### Table 2: Study Measures

			6	12
Legend: EHR: Electronic Health Record; S: Survey; M: Mobile		10	m	m
app; F: Facilitator Records	BL	wk	0	0
Flow data (recruitment, enrollment, intervention adherence and				
fidelity, data collection rates)	х	Х	Х	х
Demographic and health-related characteristics				
Demographics, physical & mental health characteristics, military				
sexual trauma screen, medication use, prior treatment for pain,				
pain over past 6 months (S, EHR)	х			
EFFECTIVENESS MEASURES				
Primary Outcome				
Pain Intensity and Interference (Brief Pain Inventory Total Score;				
BPI) (S)	х	х	х	х
Secondary Outcomes				
Physical function, anxiety, depression, fatigue, sleep disturbance,				
participation in social roles and activities, patient-ratings of				
improvement, PTSD (S)	х	Х	х	Х
Process Measures				
Medication, health care utilization related to pain treatment (S,				
EHR)	х	х	х	х
Satisfaction (S)		х		
Adverse events (S; Veteran report; events reported to C-IRB)		Х	Х	Х
Pain management self-efficacy Pain Self-Efficacy Questionnaire'				
PSEQ) (S)	х	х	х	х
Pain catastrophizing, Pain Catastrophizing Scale (PCS) (S)	х	Х	Х	Х
Applied Mindfulness Process Scale (AMPS) (S)	х	Х	Х	Х
Perceived stress (NIH Toolbox Perceived Stress Fixed Form) (S)	х	х	Х	Х

LAMP Version 16, March 25, 2024 VA Central IRB Protocol Template - version 10/26/2012 Page 41 of 60

Amount of meditation practice, app use, and class attendance (M,				
F, S)		Х	х	х
Use of non-pharmacological pain management strategies (S)	Х	Х	х	Х
COVID-19 questions	х			

**Baseline Measures** will include demographic data (assessed by self-report and the EHR) and clinical data (assessed by the EHR) to capture common mental health comorbidities (e.g., depressive disorder, PTSD, anxiety, sleep-related disorders, and substance use disorders), medication use, and prior treatment for pain. These will be assessed by the baseline survey. We will also include the Pain Management Collaboratory Coronavirus Pandemic (COVID-19) Measures, comprised of seven items assessing the potential impacts of the coronavirus pandemic.

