Process Measures/Mediators will include items to assess Capabilities, Opportunities, Motivations, and Adaptive Pain-Related Behaviors that the intervention is designed to address (delineated in our Theoretical Framework, see Figure 1). Mindfulness skills will be assessed through the Applied Mindfulness Process Scale (AMPS), a 15-item validated scale will be used to assess the extent to which participants used mindfulness practice in their daily life (e.g., to "calm my emotions when I was upset," "stop reacting to my negative impulses," "relax my body when I was tense," and "stop my unhelpful reactions to situations"). Opportunities will be assessed by the amount of training and practice participants engage in, captured by the mobile application and self-report. Motivations will be assessed by increases in pain acceptance and pain management self-efficacy and decreases in pain-related fear avoidance. Pain catastrophizing will be assessed with the Pain Catastrophizing Scale (PCS). Pain management self-efficacy will be assessed with the 8-item Pain Self-Efficacy Questionnaire (PSEQ). which has been used in numerous studies with chronic pain patients. Adaptive pain-related behaviors include reduction in opioid analgesics (assessed by EHR data) and increase in use of nonpharmacologic pain management strategies (assessed by EHR data and self-report). We also will assess perceived stress, with the NIH Toolbox Perceived Stress Fixed Form Age 18+ v2.0.

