#### General Analytic Approach.

We will use an intention-to-treat approach. Preliminary descriptive analyses will summarize the distributions of the baseline measures across treatment arms overall and by gender and will similarly assess the outcome distributions across assessment time points. We will summarize the completeness of the self-reported outcome assessments and examine associations between completeness and baseline measures as well as the association with secondary outcome assessments that are collected from the electronic medical record (e.g. medications, health care utilization related to pain treatment). In previous studies, we have observed outcome completion rates in excess of 90% at each assessment time-point. Initial analyses will use all

available follow-up data and subsequent sensitivity analyses will examine the potential effect of response bias.

For analyses of the primary outcome, all repeated measurements of the BPI score will be fitted in a mixed model for repeated measures as a function of the group assignment, while controlling for time points and baseline values of the outcome as fixed effects, with participants as random effects. Between-group differences over the entire follow-up period will be tested as the primary test of treatment group differences (this will be done for all three comparisons of the Mobile, Mobile+Group, and Usual Care arms). Between-group differences will be estimated for each of the time points (e.g. 10 weeks, 6 months and 12 months). The secondary outcomes physical function, anxiety, depression, fatigue, sleep disturbance, participation in social roles and activities, patient-ratings of improvement, and PTSD) will be similarly analyzed using the same linear mixed effect models for normal continuous measures and appropriate generalized linear mixed effect models for non-normal measures. For example, the BPI responder analyses will use generalized linear mixed effect models with binomial distributions and either log or logit links, which ever best fit the data, for the repeated dichotomous outcomes of a 30% reduction from baseline in BPI scores over the 12-month study period.

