Additional exploratory analyses involve the assessment of the extent to which amount of mindfulness practice, pain acceptance, pain-related fear avoidance, pain management self-efficacy, mindfulness skills, and perceived stress mediate the effects of the intervention. The indirect effects of these potential mediators will be tested using the bootstrap approach to obtaining confidence intervals to avoid the often-violated assumption underlying Sobel's (1982) method that the sampling distribution of the indirect effect will be normal. Similar to the methods described above for the primary analyses, weighted selection model analyses will examine sensitivity of results to response biases.

To assess the sensitivity of these initial analyses to response bias, we will fit a series of weighted selection model analyses. Each analysis will use an EM algorithm to estimate weights to assign to potential values of the missing outcomes for use in the regression model. Models will be varied to use different combinations of the following variables—intervention, observation and value of the outcome at various assessments, and baseline covariates together with pain measurements and services utilization over the follow-up period—as predictors to consider different potential missing at random and missing not at random mechanisms generating the missing data.

It has been hypothesized that men and women may respond differently to the interventions and this might be particularly true for the group-based portions of the intervention. An interaction between treatment and gender will be assessed, however tests for interaction tend to be underpowered and this is an important area of concern, so gender stratified results will be presented in secondary analyses even if statistical evidence of interaction is not found.

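### The missing-data sensitivity models leave out attendance, app use and withdrawal, so their missing-at-random versions would not adjust for losing participants who stop the programme

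*Combined protocol and SAP*

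**What the plan says.** Section 5.6, General Analytic Approach, fits all available BPI follow-up in a mixed model and then examines response bias with weighted selection models. Their predictors start with intervention and with whether the BPI was observed and its value at each assessment; the rest of the list is given as "and baseline covariates together with pain measurements and services utilization over the follow-up period". The plan states that all of these serve "as predictors to consider different potential missing at random and missing not at random mechanisms generating the missing data". The descriptive check on missing data is: "We will summarize the completeness of the self-reported outcome assessments and examine associations between completeness and baseline measures". To this it adds associations with outcomes drawn from the health record.

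Neither list names sessions attended, lessons completed, app use or withdrawal. The services term does not bring them in, because section 5.5a counts pain-related services received outside the intervention visits. Amount of practice appears in 5.6 only as an exploratory mediator.

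The data are collected, however. Table 2 has a row that begins "Amount of meditation practice, app use, and class attendance (M", where M is the mobile app. The row also names facilitator records (F) and survey (S) as sources, at 10 weeks, 6 months and 12 months. Section 5.5a adds: "Opportunities will be assessed by the amount of training and practice participants engage in, captured by the mobile application and self-report". It also provides for linking app data to VHA data by study ID, and it lists intervention adherence among the participant-flow data.

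**The concern.** For an MBI participant who returns none of the three follow-up surveys, a missing-at-random model with the listed predictors has arm, baseline and health-record data to work from. It must give that person the outcome of similar arm-mates who responded, and attenders may be over-represented among those. App and facilitator records would show whether the person had stopped, and stopping could plausibly affect both the BPI and survey return. The Introduction (2.0) itself links low adherence and attrition to reduced treatment effects.

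Usual care has no programme to stop. If stoppers do worse and are missing more often, the error therefore favours the MBI arms in primary hypotheses 1 and 2. Hypothesis 3 (Mobile+Group against Mobile) is affected only if stopping, or its link to missingness, differs between those arms; the direction cannot be told in advance.

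**Working it through.** **Inputs from section 5.6.** 200 per arm with complete data, from at least 250 randomized; effect size 0.33; alpha 0.05/3 = 0.0167; BPI SD about 2; minimal important difference about 1 point; up to 20% missing complete follow-up, with 10-15% expected. The test is taken as two-sided (not stated). The shares of stoppers, their effects and their missingness are assumptions, because the documents give none for these programmes.

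**The plan's own figure.** Power = Φ(d√(n/2) − z) = Φ(0.33 × 10 − 2.394) = 81.8% (81.4% by noncentral t), against the stated 80%. It reproduces. So 0.33 SD, or 0.33 × 2 = 0.66 BPI points, is used as the true intention-to-treat effect.

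**Illustration 1: 40% stop.** Let p be the share stopping, dA and dN the effects in attenders and stoppers, and mA and mN their missing fractions.

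- True effect = (1−p)dA + p·dN. With p = 0.4, dA = 0.55, dN = 0: 0.6 × 0.55 = 0.33 SD.
- Overall missing with mA = 0.10, mN = 0.35: 0.6 × 0.10 + 0.4 × 0.35 = 0.20.
- Available-data estimate = [(1−p)(1−mA)dA + p(1−mN)dN] / [(1−p)(1−mA) + p(1−mN)] = 0.297 / 0.80 = 0.371 SD.
- Excess: 0.041 SD, or 0.08 points (12%).
- With missingness 42.5% against 5%: 0.3135 / 0.80 = 0.392 SD, an excess of 0.12 points.
- With 10% missing overall at the same 3.5:1 ratio (mA = 0.05, mN = 0.175): 0.3135 / 0.90 = 0.348 SD, an excess of 0.04 points.
- With mA = mN the excess is zero.

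**Partial follow-up.** Illustration 1 treats every incomplete participant as missing all three surveys. The mixed model uses any visit returned. Assume correlation 0.6 between any two BPI scores. After baseline adjustment the residual correlation is (0.6 − 0.36)/(1 − 0.36) = 0.375, so a participant with one visit carries (1 + 2 × 0.375)/3 = 0.583 of the weight of one with three.

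- All incomplete participants return the 10-week survey: attenders 0.54 + 0.06 × 0.583 = 0.575; stoppers 0.26 + 0.14 × 0.583 = 0.342; estimate 0.575 × 0.55 / 0.917 = 0.345 SD.
- Half of them do: 0.5575 × 0.55 / 0.858 = 0.357 SD.
- A 600-run simulation gave 0.34 and 0.36.

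**Range at the expected missingness.** True effect 0.66 points, none in stoppers. Let q be the share stopping, m the share missing every survey, and s the share of the missing who are stoppers. The stopper share among those observed is (q − s·m)/(1 − m), and the estimate is 0.66/(1 − q) times one minus that share.

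- Low end, q = 0.3, m = 0.10, s = 0.5: 0.25/0.90 = 0.278; 0.943 × 0.722 = 0.681; excess 0.02.
- High end, q = 0.2, m = 0.15, s = 1: 0.05/0.85 = 0.059; 0.825 × 0.941 = 0.776; excess 0.12.
- Over 20-50% stopping, 10-20% missing and s from 0.5 to 1, the excess runs from 0 to 0.165 points (0 to 25%).

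**Illustration 2: attendance against an outcome tilt.** Simulation of 3,000 runs, 250 per arm, one follow-up value adjusted for baseline, 30% stopping, 20% of the MBI arm missing, about 75% of the missing being stoppers. Truth 0.66 points.

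- Missing at random without attendance: 0.77. With attendance as an imputation predictor: 0.66.
- Tilt with odds ratio 1.25 per BPI point in the MBI arm only, usual care 10% missing: 0.65.
- The same tilt in both arms, usual care 10% missing: 0.71 (0.66 at odds ratio 1.5).
- Common tilt, 20% missing in both arms: 0.77 at odds ratios 1.1, 1.25 and 1.5.

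A constructed null case (attenders +0.3, stoppers −0.7, so 0.7 × 0.3 − 0.3 × 0.7 = 0) gave an estimate of +0.11 points and 4.3% rejections, against a nominal 1.67%.

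**The case against.** A reader might infer that the planned sensitivity analyses are blind to this bias. The documents do not support that. The sentence listing the predictors includes intervention and the value of the outcome, and it provides for missing-not-at-random mechanisms. If stoppers do worse and respond less, missingness depends on the unseen BPI, which such models address. Illustration 2 shows that a suitable tilt removes the bias. What remains is narrower. The plan fixes no range and no arm-specific form. A tilt common to all arms changes nothing when missingness is equal. The data cannot identify the tilt, whereas attendance is observed.

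A reader might also carry the Introduction's attrition of up to 50% into this trial. That figure concerns standard MBSR, and these programmes were shortened partly to reduce attrition. Stopping the programme is also not the same as missing a survey: section 5.5a plans reminders by several routes with paper and phone options, each survey is paid, and 5.6 cites completion above 90% per time point in previous studies. The 20% in 5.6 means incomplete follow-up, not absence of every survey. All of this stands and lowers the likely size.

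Finally, app use is an imperfect marker. Content can be used offline or online, there is a printed workbook, and Mobile+Group views lessons in sessions while Mobile has none. Misclassification may therefore differ between the MBI arms, and the exact recovery of 0.66 assumes a perfect marker. This weakens the remedy but does not remove its value.

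**Conclusion.** The omission is confirmed, and the data to repair it are already planned. That the app and facilitator records exist for survey non-responders is inferred from their sources; the documents do not say so. If stoppers both benefit less and are missing more often, the missing-at-random sensitivity models share the upward bias of the available-data analysis. The missing-not-at-random models would reveal it reliably only with a tilt specific to the MBI arms. A common tilt helps only in so far as the MBI arms are missing more than usual care.

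The size is modest. It is zero if missingness is unrelated to stopping, about 0.02 to 0.12 BPI points at 10-15% missing with 20-30% stopping, and about 0.08 points (0.37 against 0.33 SD) with 40% stopping and 20% missing every survey. It is smaller where the 10-week survey is returned. Against a 1-point minimal important difference this would seldom change a clinical reading, and it gives no ground for calling the primary analysis invalid. It is a worthwhile, low-cost improvement to the sensitivity analyses.

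**What to change.** In section 5.6, General Analytic Approach:

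- Add to the predictors of at least one weighted selection model, within each MBI arm, the number of sessions attended or lessons completed, app use during the programme, and recorded withdrawal or termination.
- Take attendance and app use from app and facilitator records only, since self-report is missing when the survey is.
- Use these as auxiliary predictors of missingness or of missing values, not as covariates in the outcome model, and include no such terms for usual care.
- Tabulate survey completeness by attendance within each MBI arm, beside the completeness checks already planned.

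The primary model, sample size and alpha stay unchanged. The cost is a sentence or two in the plan, one table and a merge of data already collected. The downsides are a few more parameters, slightly wider sensitivity intervals, and a marker of stopping that is imperfect and may behave differently in Mobile and Mobile+Group. That last point should be noted when hypothesis 3 is interpreted.

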#### PMC COVID-19 Questionnaire Pooled Analysis Plan

We will analyze the clinical and demographic variables that are associated with a high impact from the 2019 Coronavirus pandemic. We will create a dataset (all 18 HIPAA identifiers will be removed) with clinical variables (pain scores, depression scores, suicidal ideation present), demographic variables (age, military branch, race, ethnicity, sex), and COVID-19 questionnaire variables.

A purpose of the Pain Management Collaboratory (PMC) is to support analyses of data pooled from different studies. We will contribute deidentified demographic and clinical data from the LAMP project in the PMC for analyses such as the COVID-19 analysis described above. Study participants will only be identified by a unique identifier that we will securely maintain and the other PMC research projects involved will not have access to. We will combine data from the other studies with ours to create a combined dataset for analysis. Data will be transferred from our group electronically using email and PKI encryption. Data will be stored, managed, and analyzed in the VA environment (research investigator folder and VINCI environment) by project staff on this study. We will enter into a data sharing agreement with groups sharing data that specifies (1) the information will only be used for research purposes and not to identify any individual participant; (2) the information will be secured using appropriate computer technology and (3) the data will be destroyed or returned after analyses are completed. This same request has previously been CIRB-approved for the Pain Management Collaboratory project with PIs Drs. [name] and [name].

*AIM 2 (PRE-IMPLEMENTATION):* data will be collected & described, guided by Reach, Effectiveness, Adoption, Implementation, and Maintenance (RE-AIM) framework.

#### Aim 2a: Pre-implementation data will be collected from Veteran participants via survey

We plan to collect "pre-implementation" data from a subset of intervention participants. We will conduct descriptive analyses of quantitative data separately by intervention condition (Mobile, Mobile + Group); and explore differences that may emerge by gender. Independent t-tests (for means) and z-tests (for proportions) will be used to assess group differences when appropriate. We will use Rapid Assessment Process (RAP) analyses to analyze open-ended responses

## Aim 2b: Pre-implementation data will be collected from VA employee stakeholders using rapid qualitative analysis methods.

Our qualitative data analysis strategy was developed specifically for rapid health services research. Prior to conducting any interviews, we will use our interview guide to develop an analytic matrix template, organized by topical area. Interviews will be transcribed. Guided by the transcript, we will complete a matrix for each individual interview. Matrix completion will involve summarizing the unique, substantive participant observations made during the interview for each topical area and transcribing time-stamped participant quotations illustrating each summary. After an initial matrix is completed for each interview, a combined master matrix will be created. All identified observations and illustrative quotations will be compiled into this master matrix.

## 5.7 Withdrawal of Subjects

Participants can withdraw or be terminated from the study at any point. They can withdraw from the study at any time they feel uncomfortable or choose to do so. We anticipate terminating participation if:

- 1. The participant displays abusive behavior toward other participants and/or the study staff.
- 2. Study staff believe the participant cannot meaningfully participate in the study.
- 3. Study staff believe it is not in the participant's best interest to stay in the study.
- 4. The participant becomes ineligible to participate.
- 5. The participant does not follow instructions from the researchers.
- 6. The study is suspended or canceled.
- 7. Any other condition that renders patients unable to benefit from treatment.
- 8. The participant chooses to withdraw consent.

